7.5.4.2 Assessment Period

Adverse events will be collected and monitored from the time signed informed consent/assent is obtained through the end of study (EOS) visit or 28 (+ 7) days after administration of cefiderocol in the single-dose phase or 28 (+ 7) days after administration of the last dose of study treatment (cefiderocol and SOC combination,

cefiderocol alone [if Gram-negative infection confirmed in the multiple-dose phase]) in the multiple-dose phase. If a subject withdraws early from the study or is prematurely discontinued from study treatment by the investigator, the investigator will make an effort to collect AEs for 28 (+ 7) days after administration of the last dose of study treatment. Subjects with ongoing AEs will be monitored until either resolution or stabilization is achieved, the subject is referred for continued care to another healthcare professional or until a determination of the cause being unrelated to the study treatment or study procedure is made, or the subject is lost to follow-up. Investigator causality must be included with all SAEs reported to the sponsor. Serious AEs with missing investigator causality will be followed up by the CRO urgently until a response is provided to the sponsor.

Serious adverse events occurring after the subject's completion of the study (EOS) are addressed in [Section 7.5.4.7.2](#).

7.5.4.3 Severity

The severity of an event will be graded by the investigator or subinvestigator according to the following definitions:

- **Mild:** A finding or symptom is minor and does not interfere with usual daily activities.
- **Moderate:** The event causes discomfort and interferes with usual daily activity or affects clinical status.
- **Severe:** The event causes interruption of the subject's usual daily activities or has a clinically significant effect.

All severity grades identified during the period in which the AE occurred will be recorded in the eCRF.

7.5.4.4 Relationship to the Study Treatment

The causal relationship of an event to cefiderocol will be determined by the investigator or subinvestigator according to the following criteria:

- **Related:** An AE which can be reasonably explained as having been caused by cefiderocol. For example, the occurrence of the AE can be explained by any of the following: a pharmacological effect of cefiderocol (eg, a similar event had been reported previously); an increase/decrease of the dose affects the occurrence or seriousness of the AE; or all other causative factors (eg, medical history, concomitant medication etc.) can be ruled out after careful analysis of sufficient information.
- **Not related:** An AE which cannot be reasonably explained as having been caused by cefiderocol.

Related events are defined as those events that are treatment related and treatment emergent.

7.5.4.5 Expectedness

Expected AEs for cefiderocol are listed under Expected Adverse Reactions in Section “Undesirable Effects” of the “Summary of Data and Guidance for Investigators” in the current IB for cefiderocol.

7.5.4.6 Adverse Event Assessment of Clinical Laboratory and Other Safety Parameters

For any abnormal laboratory test results (hematology, blood chemistry, or urinalysis) or other safety assessments (eg, physical examination, vital signs) that occur or worsen following exposure to cefiderocol from baseline, the investigator or subinvestigator will consider whether those results are clinically significant. Abnormal laboratory test results are defined as values outside the RR. For test results which are abnormal at baseline and significantly worsen following the initiation of the study, the investigator or subinvestigator must also consider whether those results are clinically significant. Any test results which are considered to be clinically significant by the investigator or subinvestigator are to be recorded as AEs. If abnormal laboratory finding is associated with disease or organ toxicity, the investigator should report only the disease or organ toxicity as an AE. These AEs should also be assessed as to whether or not they meet the definition of serious and should be reported accordingly.

The investigator or subinvestigator will consider test results to be clinically significant in the following circumstances (at their own discretion in the other circumstances):

- Clinical laboratory test results that lead to any of the outcomes included in the definition of an SAE ([Section 7.5.4.7.1](#)).
- Clinical laboratory test results that lead to a change in dosing of study treatment or discontinuation from the study.
- Clinical laboratory test results that lead to a concomitant drug treatment or other therapy.
- Clinical laboratory test results that require additional diagnostic testing (except for a confirmatory test) or other medical intervention.
- Clinical laboratory test results that meet the management and discontinuation criteria for abnormal liver function tests or transaminase elevations identified in [Appendix 2](#).

In addition, when any test result meets the management and discontinuation criteria for liver function abnormalities or transaminase elevations ([Appendix 2](#)), the results of further assessments and required follow-up should be recorded in the Liver Event Form in the eCRF.

7.5.4.7 Serious Adverse Events

7.5.4.7.1 Definition

An SAE is defined by regulation as any AE occurring at any dose that results in any of the following outcomes:

- Death
- Life-threatening condition
- Hospitalization or prolongation of existing hospitalization for treatment
- Persistent or significant disability/incapacity
- Congenital anomaly/birth defect
- Other medically important condition

Important medical events that may not result in death, be life-threatening, or require hospitalization may be considered as SAE when, based upon appropriate medical judgment, they may jeopardize the subject and may require medical intervention to prevent one of the outcomes listed in this definition. Examples of such medical events include allergic bronchospasm requiring intensive treatment in an emergency room or at home, blood dyscrasias or convulsions that do not result in inpatient hospitalization, or the development of drug dependency or drug abuse. Abnormal liver function tests and the process to deal with them are described in [Appendix 2](#). The investigator or subinvestigator will determine the seriousness of an AE.

An elective procedure, identified at baseline, not associated with a worsening of a known underlying medical condition is not considered an AE, and therefore will not be considered an SAE despite requiring hospitalization. However, complications of a procedure will be considered an AE and may be considered an SAE if hospitalization is prolonged (or any other SAE criteria is met). A hospitalization or prolongation of a hospitalization for reasons other than an AE would not be considered an SAE.

7.5.4.7.2 Reporting Serious Adverse Events

All SAEs must be reported to the clinical research organization (CRO)/sponsor in detail in the eCRF SAE Form in the electronic data capture (EDC) within 24 hours from the time the investigator first becomes aware of the SAE.

All SAEs must be reported regardless of causal relationship to cefiderocol and the reporter must provide a causality assessment. When reporting SAEs, the investigator should record the diagnosis whenever possible. If no diagnosis is available at the time of reporting, individual signs and symptoms can be reported.

In rare and exceptional circumstances, such as unavailability of EDC system, for reports occurring in subjects who consented but were screening failures, or for reporting instances of partner pregnancy of a male subject; sites may submit paper reports to the CRO via email or fax, within 24 hours of awareness to [REDACTED] Global Safety and Pharmacovigilance group:

Fax: [REDACTED]

Email: [REDACTED]

A template of the paper SAE Form and further instructions can be found in the Site Regulatory Binder.

Once EDC is functional again, sites must enter reports previously sent via fax or email into EDC.

If the sponsor requires a follow-up assessment, the investigator should provide new information to the CRO as it becomes available via EDC by adding the follow-up information to the SAE EDC Form. Discharge summaries, consultant reports (from other departments or other hospitals), autopsy reports, or other relevant documents must be evaluated by the investigator and all relevant information must be reported. Copies of these reports may also be requested by the sponsor.

Appropriate remedial measures should be taken by the investigator using his/her best medical judgment to treat the SAE. These measures and the subject's response to these measures should be recorded. Clinical, laboratory, and diagnostic measures should be employed by the investigator as needed to adequately determine the etiology of the event.

Investigators are not obligated to actively seek AEs or SAEs after conclusion of the study participation (EOS visit). However, if the investigator learns of SAEs occurring after the AE assessment period specified in [Section 7.5.4.2](#), considered related to cefiderocol by the investigator, the SAEs must be reported to the CRO/sponsor via email or fax at the same fax and email for reporting SAE information above in this section. Investigator assessment of causality must be included with all SAEs reported to the sponsor. Serious adverse events with missing investigator causality will be followed up by the CRO urgently until response is provided to the sponsor.

The sponsor will be responsible for reporting SAEs to the regulatory authorities as required by the applicable regulatory requirements.

7.5.4.8 Special Situations - Abuse, Misuse, Overdose, and Medication Error

All Special Situations must be reported to the CRO/sponsor's medical monitor in detail in the eCRF Special Situations Report Form in EDC as soon as possible from the time the investigator first becomes aware of the Special situation. In the event that EDC is not available, sites may submit paper reports to the CRO via email or fax at the same fax and email for reporting SAE information in [Section 7.5.4.7.2](#).

Abuse, misuse, overdose, or medication error of cefiderocol (as defined below) must be reported to the CRO or sponsor by the investigator using a Special Situations Report Form as soon as possible. If there is an associated AE, the investigator will enter the information in the eCRF and no SAE submission is required. If there are associated SAEs, the investigator will complete and submit an SAE Form in EDC as well.

- **Abuse** - persistent or sporadic, intentional excessive use of an investigational product(s), which is accompanied by harmful physical or psychological effects.
- **Misuse** - intentional and inappropriate use of an investigational product(s) other than as directed or indicated at any dose.
- **Overdose** - intentional or unintentional intake of investigational product(s) in excess of the assigned dose in the protocol.
- **Medication Error** - any unintended error in the prescribing, dispensing or administration of an investigational product(s). Cases of subjects missing doses of investigational product(s) are not considered reportable as medication error.

7.5.4.9 Pregnancy

If a female subject becomes pregnant during the study, the investigator (or subinvestigator) will immediately discontinue the study treatment. Instances of pregnancy of a female subject must be reported to the CRO in detail in the eCRF Pregnancy Test (Urine) Form in EDC within 24 hours from the time the investigator first becomes aware of the pregnancy of the female subject. Additionally, the investigator (or subinvestigator) will need to also report the completed Pregnancy paper Form via email or fax, within 24 hours of awareness, to [REDACTED] Global Safety and Pharmacovigilance group using the same fax and email procedures for SAE reporting in [Section 7.5.4.7.2](#).

Pregnancy complications and elective terminations for medical reasons must also be reported as an AE or sponsor SAE as appropriate. Spontaneous abortions must be reported as an SAE. The outcome of the pregnancy (ie, birth, miscarriage, abortion) should be followed by the investigator and must also be reported using the Pregnancy Form, which must be submitted to the CRO, if there is an issue preventing submission to the CRO.

Furthermore, the investigator must attempt to collect pregnancy information on any female partners of male subjects, who become pregnant during the study. A specific pregnant partner consent form for the pregnant partner of a male subject is available according to local regulations and must be completed prior to reporting to the sponsor information on the pregnant partner and child. Instances of pregnancy of a female partner of a male subject must be reported to the CRO via email or fax, within 24 hours of awareness, to the CRO.

Instances of pregnancy of a female partner of a male subject must be reported to the CRO at the fax number or email for SAE reporting in [Section 7.5.4.7.2](#) using the Pregnancy Form found in the Site Regulatory Binder. Pregnant Partner and Child reports must not be reported in EDC, as they pertain to individuals who are not study subjects.

Cefiderocol is not genotoxic; therefore, no requirements for male subjects to use barrier contraceptives exist.

7.5.4.10 Treatment-emergent Adverse Events

Adverse events reported after the initial dose of cefiderocol will be considered treatment-emergent AEs (TEAEs).

7.6 Efficacy Assessments (Multiple-dose Phase Only)

Microbiological response will be characterized based on microbiological laboratory results and clinical response will be characterized based on an evaluation of clinical signs and symptoms by the investigator or designee.

7.6.1 Physician Clinical Response

For the primary analysis, the clinical response will be a dichotomy (cure or failure) based on the clinical outcome as assessed by the investigator, taking into consideration objective data (eg, body temperature, white blood cell count, urinalysis).

7.6.1.1 Clinical Outcomes

The following clinical outcomes in the multiple-dose phase will be characterized at EOT, at the Posttreatment visit, and at EOS (conducted on site or as a phone call).

7.6.1.1.1 HAP/VAP/cIAI

- **Clinical Cure:** Resolution or substantial improvement of baseline signs and symptoms of pneumonia/cIAI.
- **Clinical Failure:** No apparent response to therapy; persistence or worsening of baseline signs and/or symptoms of pneumonia/cIAI; reappearance of signs and/or symptoms of pneumonia/cIAI; development of new signs and/or symptoms of pneumonia/cIAI requiring antibiotic therapy other than, or in addition to, study treatment therapy; progression of chest radiographic abnormalities; or death due to pneumonia/cIAI.
- **Indeterminate:** Lost to follow-up such that a determination of clinical cure/failure cannot be made.

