4.2 General Inclusion Criteria

Subjects who fulfill the following criteria will be included in the study.

1. Subject's parent(s) or legally authorized representative (LAR) provides written informed consent in accordance with regional and country-specific laws and regulations.
2. Subject provides written informed assent, when feasible (age of assent to be determined by institutional review boards/independent ethics committees [IRB's/IEC's] or be consistent with local legal requirements).
3. Hospitalized subject is 3 months to < 18 years of age at the time written informed consent/assent is obtained for the single-dose phase. Hospitalized subject is 3 months to < 12 years of age at the time written informed consent/assent is obtained for the multiple-dose phase. Premature babies will not be restricted, but the subject must have an adjusted or postnatal age of 3 months.
4. Subject has a suspected or confirmed infection (including but not limited to cUTI, cIAI, HAP/VAP, sepsis, or BSI) that requires hospitalization for treatment with IV antibiotics.
5. If subject is a sexually active female of childbearing potential and has reached menarche or Tanner stage 3, subject agrees to use barrier contraception (including condom, diaphragm, or cervical cap) with spermicide or agrees to use a highly effective method of contraception (including contraceptive implant, injectable contraceptive, combination oral contraceptive, or an intrauterine [IUD] contraceptive device) from Screening up to 28 days after administration of the last dose of cefiderocol.

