6.2 Concomitant Therapy

Concomitant therapy is defined as any therapy other than study treatment administered after the first dose of study treatment in the study. Concomitant medication information will be collected until the end of the study visit (EOS) in both phases of the study.

Concomitant therapy, including prescription or nonprescription medications and procedures, will be recorded in the eCRF and include the following information:

- Name of medication or procedure
- Start date
- Stop date
- Dose, dosing frequency, route of administration
- Reason for use

A concomitant antibiotic is defined as any antibiotic used to treat an infection other than the qualifying Gram-negative infection.

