7.6.2.1.1 HAP/VAP/cIAI and BSI/Sepsis

- **Eradication:** Absence of the baseline Gram-negative pathogen from an appropriate clinical specimen. If it is not possible to obtain an appropriate clinical culture and the subject has a successful clinical outcome, the response will be presumed to be eradication.
- **Persistence:** Continued presence of the baseline Gram-negative pathogen from an appropriate clinical specimen.
- **Indeterminate:** No culture obtained from an appropriate clinical specimen or additional antibiotic therapy for the treatment of the current infection including missed sampling.

7.6.2.1.2 cUTI

- **Eradication:** A urine culture shows the baseline Gram-negative uropathogen found at entry at $\geq 10^5$ colony forming units (CFU)/mL are reduced to $< 10^3$ CFU/mL.
- **Persistence:** A urine culture shows that the baseline Gram-negative uropathogen found at entry at $\geq 10^5$ CFU/mL grows $\geq 10^3$ CFU/mL.

- **Indeterminate:** No urine culture obtained or additional antibiotic therapy for the treatment of the current infection including missed sampling.

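### cIAI outcome is scored on a list shared with pneumonia and without a rule for unplanned procedures, so a child who recovers after one can be counted as a clinical cure

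*Protocol*

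**What the plan says.** cIAI is a named qualifying infection (Protocol 4.2), and efficacy is scored in the multiple-dose phase only (Protocol 7.6).

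- **Cure** for HAP, VAP and cIAI together (Protocol 7.6.1.1.1, repeated in SAP 8): "Resolution or substantial improvement of baseline signs and symptoms of pneumonia/cIAI".
- **Failure**, same block: "No apparent response to therapy; persistence or worsening of baseline signs and/or symptoms of pneumonia/cIAI"; reappearance of signs; new signs "requiring antibiotic therapy other than, or in addition to, study treatment therapy"; and, as the last items, "progression of chest radiographic abnormalities; or death due to pneumonia/cIAI".
- **Who scores and when:** the response is "based on the clinical outcome as assessed by the investigator" (Protocol 7.6.1), at EOT, Posttreatment and EOS (7.6.1.1).
- **Eradication in the protocol** (7.6.2.1.1) may be presumed without a culture: "If it is not possible to obtain an appropriate clinical culture and the subject has a successful clinical outcome, the response will be presumed to" count as eradicated. SAP 8 keeps this condition in its per-pathogen definition. Its per-subject rule does not: clinical cure at a visit makes the response eradicated for every infection except cUTI.
- **Procedures** (Protocol 6.2): "Concomitant therapy, including prescription or nonprescription medications and procedures, will be recorded in the eCRF", with dates and reason for use.

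**The concern.** A chest film cannot show whether an abdominal infection is getting worse, so for cIAI that criterion does nothing. The event that would show inadequate response in cIAI, a further unplanned operation or drainage, appears nowhere in the outcome definitions. Cure looks at how the child is at the visit and does not ask whether a further procedure was needed to get there.

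At stake are the secondary summary (cefiderocol alone) and the exploratory ones (with standard of care, and all subjects). The efficacy analyses in SAP 8.1 and 8.2 are by cohort, overall, regimen, pathogen and MIC. Infection type is summarised only as a baseline characteristic (SAP 7.2), so the cIAI children are pooled with the rest.

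**Working it through.** The plan states no figure on this point, so the check traces one child through the definitions and then sizes the effect.

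**Step 1. Apply the list.** Take a child with cIAI who responds inadequately, has an unplanned drainage after cefiderocol has started, keeps the same antibiotics, and is well at EOT.

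| Criterion (Protocol 7.6.1.1.1, SAP 8) | Met? |
|---|---|
| Cure: baseline signs resolved or much improved | Yes, at the visit |
| Failure: no response, persistence or worsening | Can be, for the time before the drainage |
| Failure: signs reappear | Only if they had settled first |
| Failure: new signs needing other or added antibiotics | No, antibiotics unchanged |
| Failure: chest radiograph | Not informative |
| Failure: death from the infection | No |

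**Step 2. Look for a tie-break.** Cure and one failure criterion can both fit. Neither document says which prevails, and neither makes a procedure a failure or an indeterminate outcome.

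**Step 3. Follow the result into microbiology.** If scored as a cure, the child becomes eradicated under the SAP 8 per-subject rule. Under Protocol 7.6.2.1.1 that happens only if a culture was not possible. Both routes need MITT membership, hence a baseline Gram-negative pathogen (SAP 5.5). SAP 6.2.3 names blood as the cIAI specimen, and material from another site counts only if the medical monitor accepts it.

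**Step 4. Size.** Protocol 3.1 plans at least 10 children in each of 3 multiple-dose cohorts: 3 × 10 = 30. Moving one child from cure to failure changes the rate by 1/n:
- cohort of 10: 1/10 = 10.0 points
- all 30: 1/30 = 3.3 points
- monotherapy group, size not given; if 3 to 8 children (assumption): 1/3 = 33.3 to 1/8 = 12.5 points.

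**Step 5. How many children?** The documents do not say. Assume a cIAI share of 10% to 40% (m = 3 to 12 of 30) and an unplanned-procedure rate r of 5% to 20%.
- Expected number = m × r: 3 × 0.05 = 0.15, up to 12 × 0.20 = 2.4.
- Chance of at least one = 1 − (1 − r)^m: 1 − 0.95^3 = 14%, up to 1 − 0.80^12 = 93%.

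These figures count children who have such a procedure. The number scored as cures can only be equal or smaller.

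**The case against.** The strongest reply is that the text does not force a cure. The investigator assigns the outcome using objective data, and the criteria for non-response, persistence or worsening require no added antibiotic and are not confined to the visit day. A reader might infer that such a child necessarily counts as a cefiderocol cure with presumed eradication. The documents do not support that: they permit it and leave the choice open. For children who also receive standard of care, the result is reported for the combination, not for cefiderocol alone. This stands, and it leaves the remaining problem that two sites can score the same case differently.

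A reader might also infer that the bias is hidden. It is not. Procedures are listed by subject and summarised by name (SAP 7.5). They are simply not tied to outcome.

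Nor does the gap arise only because cIAI shares a block with pneumonia. The cUTI and BSI/sepsis blocks have no procedure criterion either. What is particular to cIAI is that its one organ-specific criterion belongs to another organ.

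Two further points stand. Protocol 7.7 describes the efficacy assessments as supplemental and deliberately not rigorous, and Protocol 9.1 plans no inferential testing. And a rule that failed every procedure after the first dose would be wrong: cefiderocol may start within 72 hours of standard of care, so early initial source control could be caught, and the fields listed in Protocol 6.2 do not separate planned from unplanned procedures.

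**Conclusion.** The concern holds as a gap in the endpoint rule. The stated definitions allow a child with cIAI whose inadequate response led to an unplanned procedure to be counted as a cure and, in the MITT, as eradicated under SAP 8. Any resulting misclassification raises the cure rate. Each such child is worth 10 points in a cohort of 10 and 3.3 points in 30. How many there would be rests wholly on assumed shares and rates: 0.15 to 2.4 children expected over the ranges above. The outcomes affected are secondary and exploratory and are only described. The primary safety and PK objectives and the sample size are untouched.

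**What to change.** 1. Give cIAI its own outcome block in Protocol 7.6.1.1 and SAP 8, without the chest-radiograph criterion.
2. For outcome scoring, count as Clinical Failure an unplanned procedure for the qualifying infection, done for persistent, worsening or recurrent infection after the first cefiderocol dose. Let it take precedence over Cure at that visit and later ones. Exclude initial source control and procedures planned at enrolment.
3. Do not apply presumed eradication to such a child, and restore the protocol's culture condition in the SAP 8 per-subject rule.
4. Identify cases from the procedure name, dates and reason recorded under Protocol 6.2. Have the medical monitor classify each as planned or unplanned before database lock. Procedures in the 14 days before first dose, recorded under Protocol 6.1, help to separate earlier source control.
5. Show cIAI outcomes with and without these children.

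The cost is wording in two documents, a short case review and a possibly lower cIAI cure rate. The procedure records are already collected. This is a scoring rule and changes no child's treatment.
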